#### **5.2.5 Effectiveness**

To the extent possible effectiveness (or lack of effectiveness) will be inferred from patterns of treatment and re-treatment. The recommended course of etanercept treatment for paediatric psoriasis is for up to 24 weeks; physicians should consider discontinuation of etanercept if a satisfactory response is not achieved by 12 weeks.

The following data will be used to evaluate effectiveness:

- Whether a patient receives initial course of etanercept for less than 24 weeks and reason for discontinuation is not recorded as "clearing of psoriasis"
- Whether a patient is required subsequent treatment periods of etanercept or other systemic therapies after completion of initial course
- Whether a patient receives subsequent treatment periods of etanercept for less than 24 weeks
- Whether a patient has decreased disease severity after treatment with etanercept compared to baseline

## **PURPOSE SAP**

**Protocol # B1801035**

Note: Treatment for individual patients may not follow recommendations included in the product labeling, e.g., treatment with etanercept may be reported as continuous and as longer than 24 weeks initially, rather than being reported as discrete treatment periods. Any deviations from the planned analyses will be described in the interim and/or final study reports, as applicable.

### **5.3 Definition and measurement of exposure/risk windows**

#### **5.3.1 Etanercept**

##### **TREATMENT PERIODS (INITIAL AND SUBSEQUENT)**

It is anticipated that the etanercept treatment status for each patient will change throughout follow-up. A standard course of etanercept treatment is expected to last up to 24 weeks. Patients successfully responding to the first etanercept treatment course may be exposed to subsequent treatment (i.e., when patients experience a disease flare) and time window between 2 (or more) consecutive courses of treatment may vary substantially.

For the initial course of etanercept, whether the patient completed 24 weeks of treatment is recorded (yes/no), and if no, the number of weeks of treatment will be reported. Completion of initial 24 weeks of etanercept is defined as starting the first dose of etanercept within 30 day before the enrolment date or any time after enrolment date, and continuing for at least 168 days.

For each subsequent treatment period of etanercept, start and stop dates of treatment are collected. For all subsequent periods, the duration of treatment in weeks will be calculated. Cumulative exposure will be calculated by the sum, for each etanercept treatment period, of: [last dose date – first dose date] + 28. If there are less than 28 days between treatment periods, exposure will be considered uninterrupted (i.e., part of the same treatment period).

##### **CURRENT/RECENT TREATMENT VERSUS PAST TREATMENT**

In order to interpret reported events, time at risk of occurrence is established based on current or recent (within 28 days) exposure and past exposure.

**Past exposure** is defined as any exposure to etanercept, at any dose, with no reported exposure within the last 28 days.

**Current/recent exposure** is defined as on active etanercept treatment at the time of the event, or last dose of treatment within 28 days (inclusive) preceding the event.

#### **5.3.2 Other immunosuppressants and concomitant medications**

Treating physicians are asked to report information regarding use of medications, including alternative treatments for psoriasis, or other immunosuppressant and immune-modulator medications, including:

- Type of treatment or medication name
- Status of exposure to medication (i.e., current or past)

Version 5.0 dated 12Feb2019

## **PURPOSE SAP**

**Protocol # B1801035**

- Dose and duration of exposure
- Indication for use

In addition, when an opportunistic or other serious infection is reported, current/recent treatment (i.e., within 28 days) with any immunosuppressant or steroid will be evaluated.

### **5.4 Definition and measurement of covariates**

A critical element of understanding the potential association of adverse outcomes with etanercept product exposure is the inclusion of appropriate covariates in the analyses. In order to better characterize the patients who experience or do not experience the events of interest, the following additional patient characteristics and exposures with the potential to affect clinical outcomes or interpretation of the data are collected at baseline:

Demography:

- Age
- Gender
- Race/ethnicity

Related to plaque psoriasis:

- Duration of disease at baseline
- Severity of plaque psoriasis (none, mild, moderate, severe)
- Diagnosis of psoriatic arthritis
- Previous (or current) use of common plaque psoriasis therapies (topical or systemic)
- Response to previous or current therapies (none, poor, fair, good, excellent/complete, unknown)

Other covariates:

- Medical history and co-morbid conditions
- Other concomitant medications

Current plaque psoriasis disease severity, co-morbidities and all medication exposures are also collected/updated at each follow-up time point.

## **6. General Considerations for Analysis**

### **6.1 Analysis software and coding**

All AE verbatim terms will be recorded and coded using MedDRA.

All computations and generation of tables, listings and data for figures will be performed using Statistical Analysis Software (SAS)® version 9.2 or higher (SAS Institute, Cary, NC, USA).

## **6.2 Sample size**

No formal sample size calculation was performed in the design of the Registry since the goal is to obtain participation by all eligible patients. It should also be noted the study is descriptive only (i.e., non-comparative) and therefore not designed to assess differences amongst etanercept users or users of other therapies. Current available data are insufficient to project population-based estimates of paediatric patients with severe psoriasis treated with conventional systemic therapy who were not well-controlled and would warrant further intervention such as that potentially afforded by etanercept.

The best research estimates suggest that during the first 3 years following market authorization for treatment of severe disease in patients aged 8 through 17, approximately 250 patients will be treated with etanercept throughout Europe. Long-term follow-up studies, with a young and potentially highly mobile population and widely-spaced follow-up timepoints (Years 3 – 5), may incur a higher rate of loss-to-follow-up. The Registry will target 100 to 200 patients.

## **6.3 Methods for withdrawals, missing data, and outliers**

Patients may withdraw consent at any time. If a patient withdraws prior to completing the Registry follow-up period, any reason for withdrawal is to be documented. All information already collected as part of the Registry will be retained for analysis.

Several attempts will be made to contact patients and to limit missing data. In general, there will be no imputation of missing data. Data will be presented and summarized as they were recorded. However, in estimating the person-time at risk for inclusion in the sum of current/recent etanercept use, missing start or stop date of adverse events or etanercept treatment will be handled as follows:

- (1) If the day element of the start date of the most recent period of etanercept exposure is missing, it will be assumed to be the 15th of the month.
- (2) If the day element of the start date of a serious/pre-specified opportunistic infection or other SAE is missing, it will be assumed to be the 15th of the month.
- (3) If the last dose of the most recent period of etanercept exposure prior to onset of a serious/pre-specified opportunistic infection or other SAE is recorded as unknown, the reporter is asked to indicate whether it was known to be within the 28 days prior to event onset. The time at risk will be estimated to be the larger of the following: (a) time between the start date of the most recent period of etanercept exposure prior to the onset of AE and the AE onset date, and (b) 29 or (1 + 28) days.
- (4) If the month element of the event or treatment are missing, it will be assumed to be the mid of the year, i.e., July 1st.

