7.5. Missing Data

Several attempts will be made to contact patients and to limit missing data. Some imputation (e.g., in order to estimate minimum and maximum exposure) may be required. Details on handling of missing data will be included in the statistical analysis plan (SAP).

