#### **5.2.4 Treatment emergent adverse events**

Treatment emergent adverse events will be defined as events having onset date greater or equal to the first administration of Enbrel reported in the study. All events with missing start date will also be considered as treatment emergent.

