## **PURPOSE SAP**

**Protocol # B1801035**

A patient listing of all non-serious AEs and all AEs reported as possibly related to etanercept will be generated, including verbatim term and MedDRA SOC and PT, onset date, total cumulative exposure at time of onset, date of last dose of etanercept prior to onset, date of first dose of etanercept and calculated interval between last dose and onset in days [if precision of event dates allows, otherwise use response to question whether within 28 days (yes, no, unknown)].

Summaries of number of unique patients and total number of events of all reported non-serious AEs (by MedDRA SOC and PT) will also be presented.

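### SAP 6.3 sets a missing month to 1 July without bounding it by known dates, so a treatment course can stop before it starts and an event can precede first dose or enrolment

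*SAP*

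**What the plan says.** SAP 6.3 starts from no imputation and then makes an exception, "in estimating the person-time at risk for inclusion in the sum of current/recent etanercept use", with four rules. Rules (1) and (2) put a missing day on the 15th of the month. Rule (3) deals with an unknown last dose before an infection or SAE. Rule (4) reads "If the month element of the event or treatment are missing, it will be assumed to be the mid of the year" and names 1 July. It covers event dates and treatment dates alike, and no rule ties the result to a date already known. The paragraph after the rules says that missing dates will be counted and queried and their impact assessed at analysis. Sensitivity analysis is optional and not described.

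These dates feed other sections:
- SAP 6.6: time at risk per course is last dose minus first dose, plus 1, plus 28 days. For analysis, time not at risk is total follow-up minus time at risk.
- SAP 5.3.1: current/recent exposure means on treatment, or "last dose of treatment within 28 days (inclusive) preceding the event".
- SAP 7.3: infection rates are given by exposure status, with a rate ratio if each group has at least 5 infections.

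The reporter's 28-day answer appears in three places. SAP 5.2.1 and rule (3) in 6.3 request it when the date of the last dose is unknown. The listings in 7.5 and 7.6 give an interval from last dose to onset if event dates are precise enough, and "otherwise use response to question whether within 28 days (yes, no, unknown". Protocol 7.5 foresaw that "Some imputation (e.g., in order to estimate minimum and maximum exposure) may be required" and left the details to the SAP.

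**The concern.** A fixed calendar date that ignores every other date in the record can contradict that record. For treatment dates, the consequence is negative exposure time in a sum that serves as a denominator. For event dates, it is an event placed before the patient was treated or enrolled, with no instruction on what to do next.

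Exposure status then turns on a 28-day window, while the imputed date can be months away from the true one. Few events are expected, so a single allocation counts. With 5 infections in each group, moving one gives 4 and 6, and the rate ratio is no longer calculated. With 6 and 5, moving one gives 5 and 6. At fixed person-time the ratio then changes by a factor of (6/5)/(5/6) = 1.44.

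**Working it through.** The plan gives no figure for this rule, so there is none to reproduce. The first check needs only the SAP's formulas. The others use day-by-day enumeration of a 365-day year.

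**Inputs from the documents.** 1 July, which is day 182 of a 365-day year (SAP 6.3). The 28-day window (5.3.1). The time-at-risk formula (6.6). A 24-week course, from "continuing for at least 168 days" in 5.3.1; 12 weeks, the response checkpoint in 5.2.5, as a variation.

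**Assumptions not in the documents.** The year is known. True event dates and course start or stop dates are uniform over the feasible days. There is one course. The imputed event date is also used to allocate the event, since the SAP gives no other rule for allocating a year-only event in the rates.

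**1. Treatment stop with the month missing.** Start 1 September 2013, stop in 2013.
- Imputed stop 1 July: duration = -62 + 1 = -61 days; time at risk = -61 + 28 = -33 days.
- The true stop lies between 1 September and 31 December, so true time at risk is between 0 + 1 + 28 = 29 and 121 + 1 + 28 = 150 days.
- Time at risk is therefore too small by 62 to 183 days. By subtraction, time not at risk is too large by the same amount.
- Midpoint of the feasible interval, 31 October: 60 + 1 + 28 = 89 days, at most 61 days from the truth.

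**2. Event with the month missing.** First dose or enrolment on 1 October 2012 and an event later in 2012: 1 July lies 92 days before the earliest possible date. In general, for first dose on day s there are 366 - s feasible event days in that year, and all are misplaced when s > 182:
- misplaced pairs: 183 × 184 / 2 = 16,836
- all pairs: 365 × 366 / 2 = 66,795
- share: 16,836 / 66,795 = 25.2%

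**3. Exposure status.** Current/recent runs from first dose to last dose plus 28 days. An imputed date before first dose counts as not current/recent.

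| Situation in the event's year | Status wrong, 24-week course | Status wrong, 12-week course |
|---|---|---|
| Course starts that year | 46.7% | 54.5% |
| Course starts by 1 July | 28.8% | 44.3% |
| Running course ends that year | 24.7% | same (length not used) |
| On or off treatment all year | 0% | 0% |

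**4. With bounds.** Take the midpoint of first dose to 31 December instead, for the first row of the table. Placements before first dose fall from 25.2% to 0. Mean date error falls from 92 to 61 days. Wrong status falls from 46.7% to 21.5% (24 weeks) and from 54.5% to 33.1% (12 weeks). Bounds remove the impossible dates, but a year-only date remains too coarse for a 28-day window.

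**The case against.** The case on the other side is substantial, and much of it stands.

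- **Scope.** The rules are written for person-time in current/recent use, not as a general dating rule. This stands. It leaves the treatment-date problem untouched, because that is person-time. It does mean that the event-allocation result depends on the imputed date being carried into the rates.
- **Essentially arbitrary classification.** A reader might infer this from the fact that only 57 of 365 possible dates lie within 28 days of 1 July, so that the date is more than 28 days wrong for 308 of 365 (84%). That is a date error, not a misclassification rate. A large date error does no harm when exposure is constant, and SAP 5.2.5 notes that "treatment with etanercept may be reported as continuous and as longer than 24 weeks initially". Near-chance results arise only when a short course starts in the event's year.
- **28-day answer used only in listings.** A reader might infer this too, but SAP 5.2.1 links the answer to establishing exposure at infection, and rule (3) refers to it. The narrower gap is real. Section 5.3.1 does not say how the answer is applied. Rule (3) is triggered by an unknown last dose, not an unknown event month, and its formula does not use the answer. The fallback for imprecise event dates is written for listings, not for rates or the ratio.
- **Conflict with SAP 5.2.4.** That section says "All events with missing start date will also be considered as treatment emergent". Treatment-emergent status is not a person-time calculation, so rule (4) does not reach it as scoped. The SAP is silent on year-only dates there; it does not contradict itself.
- **Loss of events dated before enrolment.** Protocol 7.1 and SAP 4 define prospective events as those reported during participation. An imputed date before enrolment does not by itself exclude an event.
- **Frequency.** Follow-up is every 3 or 6 months, SAEs are notified within 24 hours of awareness, and serious infections and SAEs are adjudicated. Missing months may well be rare for these events. The 25% applies only to the year of first dose. With first dose and enrolment together and five years of follow-up, that year holds about 0.5/5 = 10% of follow-up, so about 2.5% of all month-missing events would be affected.
- **Safeguards.** Querying and counting help, but they do not correct a date that stays incomplete. The sensitivity analysis is undefined and would be chosen at analysis, under a SAP finalised in February 2019, after follow-up was due to end in 2018.

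**Conclusion.** The point holds in a limited form. Rule (4) has no bounds and, followed literally, gives impossible results: a course of -61 days (-33 days at risk), with the opposite error in time not at risk. That needs no distributional assumption.

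The rule can also date an event before first dose or enrolment (25% of month-missing events in the calendar year of first dose, uniform dates). When exposure changes during the event's year, it can misclassify current/recent versus past status (about 25% to 55% in the scenarios above, none when exposure is constant). These figures rest on the assumptions stated in the working.

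The number of month-missing records is not given and may be small, so the effect on the final rates cannot be sized. The registry is descriptive and tests no hypothesis. This is a minor correction, worth making because the rule fails where it is needed.

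**What to change.** Amend SAP 6.3 and cross-refer from 7.3 and 7.5:

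1. Bound every imputed date by the known dates. A treatment stop is not before that course's start. A prospective event is not before first dose or enrolment. Nothing falls after last contact. Within those limits, use for example the midpoint of the feasible interval.
2. Where the event date is partial, let the reporter's 28-day answer determine current/recent or past status in the incidence rates and the rate ratio, as it already does for the interval in the listings.
3. Where that answer is unknown, or was not requested because the date of the last dose was known, show the rates with the event placed in current/recent and then in past. No second version is needed if the whole feasible interval has one status.

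The third step also takes up the range idea in Protocol 7.5. The cost is a few sentences in the SAP, a small programming change and one sensitivity table. No new data collection is needed.

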## **PURPOSE SAP**

### **Protocol # B1801035**

The number of missing start or stop date of adverse events or etanercept will be examined, and its impact on analysis will be assessed at the time of analysis. Every effort will be made to query and resolve any missing data. Additional sensitivity analysis may be performed if deemed necessary.

#### **6.4 Populations for analysis**

The population for analysis includes all enrolled patients who are documented as having received at least one dose of etanercept. No internal comparator group is included in the Registry; however, where applicable, external data sources such as geographically appropriate (country-specific) population-based incidence rates (age and gender-specific) of malignancy and tuberculosis (TB) may be used to generate standardized incidence ratios (SIRs) to aid interpretation of incidence rates of malignancies and tuberculosis estimated based on data from the registry. Due to the small sample size and expected rarity of the events, this approach may be of limited value.

#### **6.5 Planned subgroups**

Descriptive analyses will be stratified, where specified, by:

- Enrollment type: Prospective (i.e., patients who started etanercept within 30 days before the enrollment date or any time after enrollment date) or retrospective
- Treatment period (initial 24 weeks/post 24 weeks/all follow-up)
- Completion of initial 24 weeks of etanercept exposure (yes/no/unknown)

Analysis of outcomes of interest:

- Etanercept exposure status (current/recent or past)
- Infection status (none during follow-up/in association with recent or current exposure/in association with past exposure)

#### **6.6 Derivations**

The following derived/calculated values will be used:

[figure not shown]
- Age at enrollment in years:  $[\text{date of enrollment} - \text{date of birth} + 1] / 365.25$
- Duration of disease at enrollment in years:  $[\text{date of enrollment} - \text{date of diagnosis} + 1] / 365.25$
- Cumulative exposure in weeks by the duration of chronic exposure for each period of etanercept exposure:  $[(\text{last dose date} - \text{first dose date} + 1) + 28] / 7$ . A treatment period is defined as continuous treatment with no interruptions of more than 28 days. Restarting treatment within 28 days is considered as having continuous exposure
- Duration of each etanercept treatment period (in weeks):  $(\text{last dose date} - \text{first dose date} + 1) / 7$
- Time at risk of malignancy (in years):  $[\text{date of malignancy diagnosis or end of follow-up if no malignancy is found} - \text{initial treatment dose date} + 1] / 365.25$

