## 7. Primary and Secondary Analyses

Evaluations and interpretations will be based on point estimates and 95% confidence intervals (CI) as evaluation of the statistical precision around the point estimate, unless otherwise specified. No formal hypothesis testing is planned. This approach follows the *Guidelines for Good Pharmacoepidemiology Practices*, Section D, point 10 [1]. Unless otherwise specified, all listings and tables are based on the total Registry population at the time of data cut-off for analysis.

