## PURPOSE SAP

### Protocol # B1801035

- Summary of patients requiring additional treatment with systemic therapy (etanercept or other non-etanercept therapies)
  - Proportion of patients requiring additional treatment, by subsequent treatment type
- Summary of overall treatment over the entire 5 years of study participation starting from enrollment to the end of follow-up.
  - Duration of exposure to etanercept
  - Cumulative dose of etanercept
  - Total number of treatment periods of etanercept [complete ( $\geq 24$  weeks), incomplete ( $< 24$  weeks) and overall]

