### **7.7 Effectiveness of treatment**

Treatment discontinuation for lack of desired therapeutic effect will, for purposes of analysis, serve as a proxy for treatment effectiveness.

A listing will be generated presenting all patients discontinuing the initial course of etanercept which will include reason for discontinuation, duration of initial course and use of previous systemic therapies.

The following summaries will also be presented:

- Summary of proportion of patients who discontinue etanercept early (< 24 weeks) due to lack of effect, AE or intolerance (primary analysis) during any period of etanercept treatment
- Summary of treatment discontinuation among all patients during any period of etanercept treatment, by each reason and in aggregate (primary analysis)
- Summary of baseline characteristics, stratified by completion/non-completion of initial 24 weeks of therapy (primary analysis)
- Summary of proportion of patients who discontinue at > 24 weeks during any period of etanercept treatment due to lack of effect, AE or intolerance (secondary analysis)
- Summary of proportion of patients who have decreased disease severity after treatment with etanercept during any period of etanercept treatment compared to baseline (as a secondary analysis) stratified by completion of initial 24 weeks.

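### SAP 7.7 names no enrolment type, so patients already on etanercept at enrolment enter its completion and severity-change summaries although they cannot meet the completion definition; a minor point is that SAP 6.6 counts duration only to the last dose

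*SAP*

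**What the plan says.** **Completion and population.** SAP 5.3.1 defines completion of the initial 24 weeks by two conditions. The first dose must fall no more than 30 days before enrolment or "any time after enrolment date, and continuing for at least 168 days". The same paragraph says that for the initial course "whether the patient completed 24 weeks of treatment is recorded (yes/no") by the site. It does not say which source governs.

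SAP 7.7 lists "Summary of baseline characteristics, stratified by completion/non-completion of initial 24 weeks of therapy (primary analysis"). As a secondary analysis it lists the proportion with lower severity than at baseline, again by completion. Neither item names an enrolment type. SAP section 7 states that, unless otherwise specified, "all listings and tables are based on the total Registry population". By contrast, SAP 7.2 names prospective patients for its exposure tables.

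SAP 6.5 defines Prospective with the same 30-day start condition and gives completion three levels, the third being unknown. It applies these strata only where specified.

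**Duration.** SAP 6.6 gives "Duration of each etanercept treatment period (in weeks") as (last dose date − first dose date + 1)/7. SAP 5.3.1 adds: "For all subsequent periods, the duration of treatment in weeks will be calculated". SAP 7.2 reports "Total number of treatment periods of etanercept", with complete meaning at least 24 weeks. SAP 5.2.5 uses as effectiveness data "Whether a patient receives subsequent treatment periods of etanercept for less than 24 weeks". Protocol 7.4 calls a course under 24 weeks premature discontinuation.

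**The concern.** Protocol 4.2 admits patients already on etanercept, whatever the length of earlier treatment. Under the SAP 5.3.1 definition, a child treated for a year before enrolment is not a completer. In a table with the two levels completion and non-completion, that child could sit beside children who stopped early. The table is labelled primary, and premature discontinuation is part of a stated registry objective (protocol section 2). Mixing the two groups would blur the comparison that the table is meant to give.

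The severity summary has a related weakness. If baseline severity for these patients is recorded after weeks or months of treatment, part of any response has already happened. On the four-level scale in SAP 5.4, a patient already at 'none' cannot improve at all.

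The duration formula raises a smaller matter. A sharp cut-off is placed at the length of a standard course, and the formula gives no credit for the days covered by the last dose.

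**Working it through.** **1. Who can be a completer**

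- The plan's day count reproduces: 24 × 7 = 168 days.
- The start condition in SAP 5.3.1 is also the Prospective condition in SAP 6.5. Every retrospective patient therefore fails the definition, whatever the treatment length.
- SAP 7.7 specifies no population, so the SAP section 7 default brings these patients in. They go to non-completion (the only other level in the 7.7 baseline item) or to unknown (SAP 6.5). The text does not say which. If the site item governs instead, such a patient could be recorded as yes, against the definition.

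**2. Which baseline severity they have**

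- SAP 5.4 lists severity among the items collected at baseline, and SAP 5.1 places baseline at enrolment.
- Protocol 6.2.1, item 8, lists what is abstracted retrospectively: dosing history, other systemic therapies, infections and SAEs. Pre-treatment severity is not on that list.
- On this reading the reference value is an on-treatment value. If treatment lowers severity on average, improvement from that value is understated.

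**3. Size**

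The documents do not give the number of retrospective patients, and protocol 6.2 expects it to be limited. With the 60 to 80 patients of protocol section 3 and SAP section 4, one patient is 1/80 = 1.25% to 1/60 = 1.67% of the registry, and a larger share of any one stratum. SAP 6.2 still gives a target of 100 to 200; on that figure one patient is 0.5% to 1.0%.

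**4. Duration**

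Let d be last minus first dose date in days. SAP 6.6 reaches 24 weeks if (d + 1)/7 ≥ 24, that is d ≥ 167. The registry fixes no regimen (protocol section 5), so the dosing intervals are assumptions. Weekly is the regimen of the paediatric psoriasis trial and twice weekly that of the JIA experience, both in protocol 1.1. Twice weekly is taken as alternating gaps of 3 and 4 days.

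| Doses | d | Weeks by 6.6 | Class |
|---|---|---|---|
| 24 weekly, on schedule | 23 × 7 = 161 | 162/7 = 23.14 | under 24 |
| 25 weekly, on schedule | 24 × 7 = 168 | 169/7 = 24.14 | at least 24 |
| 24 weekly, one week missed | 22 × 7 + 14 = 168 | 169/7 = 24.14 | at least 24 |
| 48 twice weekly, 3-day gap first | 24 × 3 + 23 × 4 = 164 | 165/7 = 23.57 | under 24 |
| 48 twice weekly, 4-day gap first | 24 × 4 + 23 × 3 = 165 | 166/7 = 23.71 | under 24 |

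If one dosing interval is added after the last dose, the condition becomes d + interval ≥ 168:

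- With 7 days, periods with d = 161 to 166 change class.
- With 4 days, periods with d = 164 to 166 change class.
- The 7-day rule does not suit twice-weekly dosing. There, 47 doses span 23 × 7 = 161 days, and (161 + 7)/7 = 24.00 would count as complete, against (161 + 4)/7 = 23.57 with 4 days.

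**5. Cut-offs**

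SAP 7.2 uses ≤24 and >24 weeks for the initial course but ≥24 and <24 for counting periods. SAP 7.7 uses <24 and >24. A period of exactly 24.00 weeks has no place in 7.7. That is the value 24 weekly doses take once an interval is added: (161 + 7)/7 = 24.00.

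**The case against.** **On the population.** The table shells are not in the documents. The SAP document history records a retrospective-patients column added to the T2, T3 and T4 series, so the 7.7 tables may already be split. Protocol 7.3 summarises baseline data by status at enrolment, and protocol 7.6 discusses how already-treated patients may differ. Severity change is assessed only if the data exist for the majority of patients (SAP section 4), and it is secondary. Protocol 7.3 can also be read as describing severity before the first dose. All of this limits the point. It does not remove it, because the 7.7 text carries no split and gives these patients no level.

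A reader might infer that they will be tabled as non-completers. The documents do not establish that; unknown is also possible. A reader might also try to size the understatement from the response rates in protocol 1.1. Those rates come from different patient groups (the later one follows an extension in which all patients received etanercept) and from a different severity index, so they cannot size it.

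**On duration.** Counting from first to last dose inclusive is a recognised convention, and protocol 7.4 anchors treatment time on the same two dates. It is not an arithmetic error. A reader might infer that completion is possible only from the 25th weekly dose. That is true only on schedule: 24 doses with one missed week already score 24.14 weeks.

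The initial course may be protected by the site's yes/no item. The 7.7 early-stop proportion also requires lack of effect, AE or intolerance as the reason, so the formula touches it only at the margin. These objections stand, and they reduce the duration point to a sensitivity question.

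**Conclusion.** The main point holds for the SAP text. Retrospective patients enter the 7.7 completion-stratified and severity-change summaries by default, cannot satisfy the completion definition, and appear to have an on-treatment severity baseline. The bias in severity change is towards understating improvement. Its size cannot be computed, because neither the number of such patients nor their pre-treatment severity is given; few are expected. The conclusion assumes that baseline severity is the value at enrolment and that the unseen shells do not already make the split.

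The duration point is minor. An on-schedule course of 24 weekly or 48 twice-weekly doses is classed as under 24 weeks in SAP 7.2, SAP 5.2.5 and the protocol 7.4 frequency. This matters mainly for subsequent periods, whose duration is calculated. It assumes no delayed or missed doses, and that the stop date collected under SAP 5.3.1 is the date of the last dose. If sites enter the end of coverage instead, the effect shrinks. How many periods have spans of 161 to 166 days is unknown, but the sponsor can count them. The material does not support replacing the formula. No view is taken on dosing or course length.

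**What to change.** 1. In SAP 7.7, present the completion-stratified baseline table and the severity-change summary by the SAP 6.5 enrolment type. Make Prospective the main display, show retrospective patients separately, and do not count them as non-completers. State that this departs from the SAP section 7 default.
2. In SAP 5.3.1, state whether the site's yes/no item or the 168-day derivation governs the initial course.
3. Keep the SAP 6.6 formula and the 28-day exposure window. Add a sensitivity count with one dosing interval after the last dose (7 days for weekly, 4 days for twice weekly), and report how many periods change class. Where the regimen is not recorded, show the count both ways.
4. Use <24 versus ≥24 weeks throughout SAP 7.2 and 7.7.

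The cost is SAP text and some programming. No new data are needed, which matters because follow-up was due to end in 2018 and this SAP version is dated February 2019. The price is fewer patients in the main 7.7 display. The regimen is listed at baseline and in the retrospective dosing history but not among the follow-up items (protocol 6.2.1 and 6.2.2), so later periods may need both intervals.
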